6.4.8 Pachymetry

Automated pachymetry will be performed to measure the corneal thickness. The average and standard deviation (if available) will be recorded for the central cornea. There are no restrictions on the type of pachymeter used in collection of data for this study although automated reading from the specular microscope is preferred; the same methodology must be used consistently within a subject. For those pachymeters that are not self-calibrating, calibration must be performed on a quarterly basis and documented in the calibration log in the study regulatory binder.

6.4.9 Intraocular Pressure Measurement

IOP must be recorded using Goldmann Applanation Tonometry (GAT). At least two measurements will be obtained and recorded (a third measurement will be obtained if there is a \geq 3 mmHg difference between the first two measurements). Post-dose IOP will be measured at least every 30 minutes until normalized (defined as less than 5 mmHg higher than pre-injection IOP).

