(including automated pachymetry)					i							
Pentacam examination				OU	1						OU	
Best corrected visual acuity ^b			OU	SE	!		SE	SE	SE	SE	SE	SE
Slit lamp biomicroscopy			İ	SE	1		SE	SE	SE	SE		SE
Intraocular Pressure (IOP) measurement				SE e	SE e		SE ^e	SE e	SE ^e	SE	SE	SE

OU=both eyes, SE=Study Eye, a Perform prior to any other assessments, b If subject is to be dilated, perform prior to dilation, c 2

timepoints (1 in the early morning and 1 in the late afternoon), may be different days.^d e IOP pre-dose and post-dose at least every 30 minutes until normalized (defined as less than 5 mmHg higher than pre-injection IOP), ^f dilated exam only in subjects with vitreous in the AC at baseline

*Including all ocular medications

LIST OF ABBREVIATIONS

ADA	Anti-Drug Antibody
AE	Adverse Event
BCVA	Best Corrected Visual Acuity
CEC	Corneal Endothelial Cell
CED	Corneal Endothelial Dystrophies
CIARC	Cornea Image Analysis Reading Center
CRF/ eCRF	Case Report Form/ electronic Case Report Form
CRO	Contract Research Organization
DHHS	Department of Health and Human Services
DLT	Dose limiting toxicity
DMEK	Descemet Membrane Endothelial Keratoplasty
DSEK	Descemet Stripping Endothelial Keratoplasty
ECD	Endothelial Cell Density
EDC	Electronic Data Capture
eFGF-1	engineered FGF-1
ETDRS	Early treatment diabetic retinopathy study
FDA	Food and Drug Administration
FECD	Fuchs Endothelial Corneal Dystrophy
FGF	Fibroblast Growth Factor
GAT	Goldmann Applanation Tonometry
GCP	Good Clinical Practice
HED	Human Equivalent Dose
IC	Intracameral
ICF	Informed consent form
ICH	International Conference on Harmonisation
IOP	Intraocular pressure
IRB	Institutional review board
ITT	Intent to Treat
IUD	Intrauterine device
LOCF	Last Observation Carried Forward
MMRM	Mixed Model Repeated Measures
MRSD	Maximum Recommended Starting Dose
NEI-VFQ	National Eye Institute Visual Function Questionnaire
NOAEL	No Observable Adverse Event Level
PAD	Pharmacologically Active Dose
РК	Pharmacokinetic
PP	Per Protocol
SAE	Serious Adverse Event
SAR	Suspected Adverse Reaction
SE	Study Eye
ТМ	Trabecular Meshwork
WOCBP	Women of Childbearing Potential
wtFGF-1	Wild type FGF-1

TABLE OF CONTENTS

Docu	men	t History
Synop	osis.	
List o	f Ab	breviations
1.	Int	roduction12
1.1	C	Corneal Endothelial Dystrophy
1.2	Т	Treatment Options
1.3	F	GF for the Treatment of Corneal Endothelial Dystrophy 12
1.4	Γ	Diurnal Variation in Ocular Function
2.	Bac	ckground Information
2.1	I	nvestigational Product TTHX1114(NM141)13

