4.5 Dose Escalation/ Cohort Review

The unmasked Medical Monitor will review all available clinical data when the last subject of the first cohort of subjects completes the Day 7 examinations before enrollment in the second cohort may start. Then, the unmasked Medical Monitor will review clinical data when the last subject in the second cohort completes the Day 7 examinations before enrollment into the third

Trefoil Therapeutics, Inc.	Clinical Study Protocol TTHX-001
Confidential and Proprietary	Amendment 1.0: September 8, 2020

cohort may start. If, at any time, the safety profile is deemed unacceptable, treatment will revert to the prior lower-dose level which was deemed safe.

4.5.1 **Dose Limiting Toxicities**

Potential dose limiting toxicity (DLT) is defined as any of the following events:

- Visual acuity loss of 15 ETDRS letters or more
- > 5 anterior chamber cells observed on slit lamp examination
- > 10 vitreous cells observed on slit lamp examination
- >710 micron corneal thickness or a 150 micron increase from baseline (Day 0 pretreatment)
- Increase of 2 or more grades in conjunctival hyperemia
 - Grade 0 = No vasodilation (Absent)
 - \circ Grade 1 = Some vasodilation
 - Grade 2 = Extensive vessel vasodilation
 - Grade 3 = Overall vasodilation
- IOP that remains higher than 32 mmHg and not responding to therapy

If any subject experiences any of the events listed above, study treatment must be held for at least 7 days, and the masked Medical Monitor must be contacted to discuss medical management of the subject including possible treatment and additional unscheduled study assessments.

After the 7-day study treatment delay, the subject may receive additional study treatment if the subject remains eligible and all of the potential DLTs the subject experienced have decreased to a level that no longer meets the DLT requirements. Any of the events listed above that continue to meet the DLT requirements after the 7-day delay in study treatment will be considered DLT and the subject will be discontinued from study treatment. Any study treatment delay of greater than 7 days must be discussed with and approved by the masked Medical Monitor.

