5.2 Exclusion Criteria

- 1. History of any of the following in either eye:
 - a. Ocular cancer (including melanoma)
 - b. Herpetic keratitis
 - c. Corneal transplant (full-thickness or lamellar)
 - d. Documented and repeated elevated IOP in either eye
 - e. Posterior Polymorphous Corneal Dystrophy (PPCD; aka Schlichting dystrophy)
 - f. Uveitis
 - g. Cataract surgery within the 3 months in prior to Study Day 0
- 2. Refractive surgery in the study eye, including phakic IOL currently in place Note: Potential subjects who have had the phakic IOL placed and removed are allowed. Limbal relaxing incision performed at the time of cataract surgery is allowed
- 3. Any condition that would impair examination of the anterior chamber structures in the Study Eye
- 4. Anterior Chamber IOL placement (in the Study Eye)
- 5. Expected or planned ocular surgery (incisional or laser) in the Study Eye within the next 3 months (including endothelial keratoplasty)
- 6. Use of systemic or dermatological cytotoxic chemotherapy within the 1 month prior to or planned use within the 3 months following Study Day 0

Trefoil Therapeutics, Inc.	Clinical Study Protocol TTHX-001
Confidential and Proprietary	Amendment 1.0: September 8, 2020

- 7. Use of hypertonic saline eye preparations (e.g.; Muro 128) within the 3 days prior to Study Day 0 (either eye)
- 8. Active extra-ocular inflammation from any non-infectious or infectious cause (bacterial, viral or fungal) in the Study Eye within the 6 months prior to Study Day 0

Note: Mild blepharitis and/or dry eye related inflammation are allowed

- 9. Treatment with a rho kinase inhibitor within the last 3 months (either eye)
- 10. Use of cyclosporine ophthalmic emulsion (e.g.; RESTASIS®) within the 30 days prior to Study Day 0 (either eye)
- 11. Use of Xiidra® (lifitegrast ophthalmic solution) within the 30 days prior to Study Day 0 (either eye)
- 12. Systemic (nasal, inhaled, oral, parenteral, or topical) or ophthalmic corticosteroid use in the 30 days prior to Study Day 0 unless approved by the Medical Monitor

Note: Potential subjects on a stable chronic low-dose that is not expected to change in the 3 months following Study Day 0 may be considered for the study after approval by the Medical Monitor

13. History of significant allergy, hypersensitivity, or intolerance to any drug compound, food, or other substance

Note: This includes all components and excipients of the study drug

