6.5.1 Screening Period/Baseline Assessments

Screening assessments may be performed anytime during the Screening Period unless otherwise specified.

Screening

- Informed consent
- Eligibility assessment
- Demographics
- Medical and Ocular History
- Record Concomitant Medication Use
- BCVA
 - Both eyes
 - Between 07:00 AM and 11:00 AM
- Specular Microscopy (including automated pachymetry)
 - Both eyes
- Comprehensive Ocular Examination
 - Slit-lamp biomicroscopy
 - Dilated examination of lens, fundus, and vitreous
 - Both eyes

Note: Subjects enrolled in and participating in the Observational Sub-study who are eligible may "roll-over" into the main study provided they meet all of the additional eligibility criteria,

Trefoil Therapeutics, Inc.	Clinical Study Protocol TTHX-001
Confidential and Proprietary	Amendment 1.0: September 8, 2020

there is an open cohort, and they consent. Observational Sub-study assessments may be used as screening assessments for the main study as long as they were performed within the protocol-specified timeframe.

6.5.2 Day 0

Pre-Injection

- Record Concomitant Medication Use
- Urine pregnancy (WOCBP)
- Obtain samples for laboratory testing:
 - Collect samples for Chemistry, Hematology, Urinalysis, HbA1c, per the TTHX-001 Laboratory Manual
 - Collect optional blood sample for genetic testing (if consented)
- Obtain sample for ADA
- Obtain sample for PK
- NEI-VFQ-25
- Best corrected visual acuity (BCVA)
 - Study eye
 - Between 07:00 AM and 11:00 AM
- Specular Microscopy (including automated pachymetry)
 - Both eyes
- Slit Lamp Biomicroscopy
 - Study eye
- IOP
 - Study eye
- Pentacam examination
 - Both eyes
- Confirm eligibility

Post-Injection

- IOP
 - Study eye only
 - At least every 30 minutes after injection until normalized (within 5 mmHg of pre-injection measurement)
- Record Adverse Events and Concomitant Medication Use
- 6.5.3 Day 3
 - Record Adverse Events and Concomitant Medication Use. This visit may be conducted by phone.

6.5.4 Day 7 ± 1

- BCVA
 - Study eye only
 - Between 07:00 AM and 11:00 AM
 - Pre-injection

Trefoil Therapeutics, Inc.	Clinical Study Prot
Confidential and Proprietary	Amendment 1.0: Se

- Specular Microscopy (including automated pachymetry)
 - \circ Both eyes
 - Pre-injection
- Slit Lamp Biomicroscopy
 - Study eye only
 - Pre-injection
- IOP
 - Study eye only
 - Pre-injection
 - At least every 30 minutes after injection until normalized (within 5 mmHg of pre-injection measurement)

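### The post-injection IOP checks end by comparison with that day's pre-injection value and have no absolute ceiling, so in a rare eye with a high starting pressure they can end above 32 mmHg

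*Protocol*

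**What the plan says.** Section 6.4.9 sets the rule: after each dose, IOP is read at least every 30 minutes "until normalized (defined as less than 5 mmHg higher than pre-injection IOP"). Footnote e of the schedule in the synopsis and of the schedule in Appendix A repeats that definition. The visit lists for Days 0, 7, 14 and 21 (sections 6.5.2 and 6.5.4 to 6.5.6) word it slightly differently, as "within 5 mmHg of pre-injection measurement". In every version the reference is the reading taken before that day's injection.

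The only absolute IOP figure is in section 4.5.1, where one of the potential dose-limiting toxicities is "IOP that remains higher than 32 mmHg and not responding to therapy".

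On the starting pressure, exclusion 1d removes patients with a history of "Documented and repeated elevated IOP in either eye", with no number attached. Section 4.4.1 allows further injections while the subject remains eligible and has had no DLT, and sets no IOP limit. The Day 3 contact in section 6.5.3 lists no IOP, and "This visit may be conducted by phone".

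**The concern.** A purely relative rule detects a rise caused by the injection, but it does not ask whether the pressure at which checking stops is acceptable. In an eye that starts high, the rule can call a pressure normalized when it is above the protocol's own 32 mmHg level.

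The section 4.5.1 criterion depends on whether a high pressure persists and whether it responds to therapy. Both need repeat readings, and in such an eye the mandatory same-day repeats end before either has been assessed.

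The reference value also moves. On Days 7, 14 and 21 it follows earlier injections, so if treatment raised IOP the stopping limit would rise with it.

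What is at stake is that subject's follow-up on the day of injection, in a first-in-human study with safety in its primary objective.

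**Working it through.** **Inputs**
- Stopping rule: post-injection minus pre-injection IOP below 5 mmHg (6.4.9 and both footnotes e), or within 5 mmHg (visit lists).
- Absolute level: 32 mmHg (4.5.1).
- Injections: 71 subjects × 4 = 284 (section 4, Table 1; section 4.3).
- Visit windows: Days 7, 14, 21 and 28, each ±1 day.
- IOP distribution: not given in the protocol, so assumed below.

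**Starting pressure at which checks can end above 32 mmHg**

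Checks end when post < pre + 5. Ending with post > 32 requires pre + 5 > 32, so pre > 32 − 5 = 27 mmHg.

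With whole-mmHg readings the lowest value above 32 is 33:
- Under the 6.4.9 wording, 33 < pre + 5 gives pre ≥ 29 (33 − 29 = 4, which is below 5).
- Under the visit-list wording, read as inclusive, 33 ≤ pre + 5 gives pre ≥ 28.
- Example: pre 30, post 34, difference 4. The checks may end at 34 mmHg.
- At pre 27 the checks end below 32 (at most 32 under the inclusive reading), so the problem cannot arise at 27 or less.

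**Whether anything readable prevents such a starting value**

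Exclusion 1d needs an elevation that is both documented and repeated. The main-study screening lists (6.1, 6.5.1) and the screening column of Appendix A contain no IOP, and the comprehensive examination in 6.4.4 is defined as slit lamp plus dilated examination. Unless a subject rolls over from the sub-study, the first scheduled IOP is the Day 0 pre-injection reading. A single high reading does not by itself meet 4.5.1, so it does not automatically hold an injection.

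**How often (assumptions)**

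Pre-injection IOP is taken as normal, with no drug effect on IOP. Expected number = 284 × tail probability. Whole-mmHg thresholds use cut-offs of 27.5 and 28.5.

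| Pre-injection IOP | Mean 16, SD 4: probability | Expected of 284 | Mean 15.5, SD 3: probability | Expected of 284 |
|---|---|---|---|---|
| > 27 | 0.00298 | 0.85 | 0.000063 | 0.018 |
| ≥ 28 | 0.00202 | 0.57 | 0.000032 | 0.009 |
| ≥ 29 | 0.00089 | 0.25 | 0.000007 | 0.002 |

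Under these assumptions the figures are upper bounds, because the post-injection reading must also be above 32 and within the stopping limit. At pre 29, under the 6.4.9 wording, only 33 qualifies; at pre 30, only 33 or 34.

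**Time to the next scheduled IOP**
- After Day 0: Day 7 ± 1, so 6 to 8 days.
- After Days 7, 14 and 21: both visits can move by one day, so 7 ± 2 = 5 to 9 days.

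**The case against.** The strongest case against is that this is a preference rather than a defect. A comparison with that day's pre-injection value suits a check meant to detect an injection-induced rise. Section 4.5.1 requires persistence and failure of therapy, so a single 33 or 34 mmHg is not a DLT, and the protocol never makes 32 mmHg a level for ending checks. Investigators see the pre-injection reading before dosing, may exclude or stop a subject on judgement (exclusion 17, section 5.3), may measure more often than every 30 minutes, and may call unscheduled visits (section 6.5.11). Part of the injection procedure in section 6.2 is not readable and could contain a pressure check. The affected eye may never occur: with whole-mmHg readings and the 6.4.9 wording, the upper bound is only 0.002 to 0.25 injections in the trial.

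Much of this stands. There is no contradiction with 4.5.1, the event is rare, and the absence of a ceiling is established only for the readable text. Readings are recorded, and IOP is measured again before each later dose and at Days 28, 56 and 90, so no missed or unrecorded DLT is claimed.

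The safeguards, however, are discretionary, whereas the stopping rule is the written minimum. As written, that minimum lets mandatory follow-up end at 34 mmHg after a starting value of 30.

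It is also fair that an added ceiling does not address the decision to inject an eye at 29 or 30 mmHg. It addresses only what happens afterwards.

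**Conclusion.** The point holds and is minor. As written, the mandatory post-injection checks can end above 32 mmHg whenever the pre-injection IOP exceeds 27 mmHg (whole readings: at least 29, or at least 28 under the visit-list wording), with no further scheduled IOP for 5 to 9 days. Fewer than one of the 284 planned injections is expected to start that high under either assumed distribution. Those frequencies rest on assumed normal distributions and no drug effect; a treatment-related rise in IOP would make qualifying starting values more common. The conclusion concerns one subject's same-day safety follow-up and says nothing about DLT counts or dose escalation.

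**What to change.** Define normalized as less than 5 mmHg above the pre-injection IOP and not above 32 mmHg. Use the same wording in section 6.4.9, the visit lists in 6.5.2 and 6.5.4 to 6.5.6, and footnote e of both schedules. This also removes the small mismatch between the two existing wordings.

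The ceiling uses the protocol's own figure and changes nothing when the pre-injection IOP is 27 mmHg or less. The cost is one added clause in each place. Occasionally a subject with a high starting IOP will stay for further 30-minute readings or be treated before leaving. An eye already above 32 mmHg before injection would have to fall below its starting value before checks could end. That is a deliberate change in what the term means.

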6.4.10 Urine Pregnancy Test

WOCBP must be tested prior to the start of study treatment and after the completion of study treatment to confirm a continued non-pregnant state. Commercially available urine dip-stick pregnancy tests are acceptable.

6.4.11 Clinical Laboratory Assessments

Samples for clinical laboratory assessments will be obtained and transmitted to a central laboratory. The laboratory parameters to be tested are summarized below in Table 4.

All clinically significant laboratory results that are outside of the normal ranges are to be reported as AEs. An abnormal lab value should be deemed clinically significant if either of the following conditions is met:

• The abnormality suggests a disease and/or organ toxicity that is new or has worsened from baseline as determined by the Investigator and in consultation with Medical Monitor consult at the Investigator's request

Trefoil Therapeutics, Inc.	Clinical Study Protocol TTHX-001
Confidential and Proprietary	Amendment 1.0: September 8, 2020

• The abnormality is of a degree that requires additional active management, e.g., change of dose, discontinuation of the drug, close observation, more frequent follow-up assessments, or further diagnostic investigation

Therefore, a clinically significant laboratory value is one that suggests a new disease process, an exacerbation or worsening of an existing condition, or requires further action(s) to be taken.

If a clinically significant laboratory result is found on a laboratory test (e.g., hematology), the Investigator should determine if an underlying condition is the reportable AE instead of the individual laboratory parameters (e.g., anemia instead of decrease in red blood cell count, hematocrit, reticulocyte and hemoglobin levels).

Table 4: Clinical Laboratory Assessments

Hematology		
Hematocrit		
Hemoglobin		
• White blood cell (WBC) count with differential		
Platelet count		
Serum Chemistry	Urinalysis	
Albumin	Specific gravity	
Alkaline phosphatase	• Ketones	
 ALT (alanine amino transferase)/ SGPT 	• pH	
• AST (aspartate amino transferase)/ SGOT	• Protein	
Bicarbonate/CO2	• Glucose	
• Bilirubin	• Blood	
Blood urea nitrogen	• Urobilinogen	
Calcium	• Bilirubin	
• Chloride	Leukocyte esterase	
• Creatinine	• Microscopic examination (as applicable)	
• HbA1-c		
• LDH (Lactate dehydrogenase)		
Potassium		
• Sodium		
Total protein		
Uric acid		

6.4.12 Plasma for PK and ADA

Blood samples will be collected for pharmacokinetic (PK) and anti-drug antibody (ADA) analysis. Samples will be centrifuged and/or prepared per instructions from the analytic laboratory. Pre-injection samples should be collected within the 2 hours prior to study treatment administration. PK samples should be collected within ± 5 minutes of the nominal timepoint or as soon as practicable.

See Study TTHX-001 Laboratory Manual for blood processing instructions.

6.4.13 National Eye Institute Visual Function Questionnaire (NEI-VFQ-25)

The NEI-VFQ-25 is a reliable and validated 25-item version of the 51-item NEI-VFQ [16]. The subject will complete the NEI-VFQ-25 at Day 0 (pre-injection) and Day 56. The NEI-VFQ-25 is to be completed prior to any other procedures at these visits. Upon completion of the

Trefoil Therapeutics, Inc.	Clinical Study Protocol TTHX-001
Confidential and Proprietary	Amendment 1.0: September 8, 2020

questionnaire, the study coordinator will check the questionnaire for completeness. Any omissions or ambiguous answers will be clarified by the subject prior to leaving the clinic. The NEI-VFQ-25 should be self-administered, however, trained investigational site staff will administer the questionnaire to subjects who are unable to self-administer the questionnaire.

6.4.14 **Pentacam Tomography**

Pentacam® tomography must be performed during screening and at Study Day 56. The Pentacam images must meet the internal software quality metric to be acceptable.

6.4.15 **Optional Blood Sample for Genetic Testing**

Subjects with a diagnosis of FECD will be asked to provide an optional blood sample for genetic testing. Subjects will be asked to provide specific consent for this optional genetic testing. This sample will be completely de-identified prior to transmittal to the testing facility. This sample is optional and participation in neither the Observational Sub-study nor the interventional portion is conditional on the consent to provide this sample for genetic testing.

6.5 Study Visits

All study visits/ assessments will be conducted by qualified investigational site staff. Study visits/ assessments are to be conducted within the protocol-specified window for each visit/ assessment. If an assessment is not able to be collected within the protocol-specified window, it should be collected as soon as practicable and the actual date/ time recorded. Comparative assessments should be collected at the same time at each timepoint, when possible (unless otherwise directed). If an onsite visit is not possible, as many assessments as feasible can be conducted remotely.

6.5.1 Screening Period/Baseline Assessments

Screening assessments may be performed anytime during the Screening Period unless otherwise specified.

Screening

- Informed consent
- Eligibility assessment
- Demographics
- Medical and Ocular History
- Record Concomitant Medication Use
- BCVA
 - Both eyes
 - Between 07:00 AM and 11:00 AM
- Specular Microscopy (including automated pachymetry)
 - Both eyes
- Comprehensive Ocular Examination
 - Slit-lamp biomicroscopy
 - Dilated examination of lens, fundus, and vitreous
 - Both eyes

Note: Subjects enrolled in and participating in the Observational Sub-study who are eligible may "roll-over" into the main study provided they meet all of the additional eligibility criteria,

Trefoil Therapeutics, Inc.	Clinical Study Protocol TTHX-001
Confidential and Proprietary	Amendment 1.0: September 8, 2020

there is an open cohort, and they consent. Observational Sub-study assessments may be used as screening assessments for the main study as long as they were performed within the protocol-specified timeframe.

6.5.2 Day 0

Pre-Injection

- Record Concomitant Medication Use
- Urine pregnancy (WOCBP)
- Obtain samples for laboratory testing:
 - Collect samples for Chemistry, Hematology, Urinalysis, HbA1c, per the TTHX-001 Laboratory Manual
 - Collect optional blood sample for genetic testing (if consented)
- Obtain sample for ADA
- Obtain sample for PK
- NEI-VFQ-25
- Best corrected visual acuity (BCVA)
 - Study eye
 - Between 07:00 AM and 11:00 AM
- Specular Microscopy (including automated pachymetry)
 - Both eyes
- Slit Lamp Biomicroscopy
 - Study eye
- IOP
 - Study eye
- Pentacam examination
 - Both eyes
- Confirm eligibility

Post-Injection

- IOP
 - Study eye only
 - At least every 30 minutes after injection until normalized (within 5 mmHg of pre-injection measurement)
- Record Adverse Events and Concomitant Medication Use
- 6.5.3 Day 3
 - Record Adverse Events and Concomitant Medication Use. This visit may be conducted by phone.

6.5.4 Day 7 ± 1

- BCVA
 - Study eye only
 - Between 07:00 AM and 11:00 AM
 - Pre-injection

Trefoil Therapeutics, Inc.	Clinical Study Prot
Confidential and Proprietary	Amendment 1.0: Se

- Specular Microscopy (including automated pachymetry)
 - \circ Both eyes
 - Pre-injection
- Slit Lamp Biomicroscopy
 - Study eye only
 - Pre-injection
- IOP
 - Study eye only
 - Pre-injection
 - At least every 30 minutes after injection until normalized (within 5 mmHg of pre-injection measurement)
- Study Treatment IC Injection (SE) ۲
- Record Adverse Events and Concomitant Medication Use •

6.5.5 Day 14 ± 1

- BCVA •
 - Study eye only
 - Between 07:00 AM and 11:00 AM
 - Pre-injection
- Specular Microscopy (including automated pachymetry)
 - Both eyes
 - Pre-injection
- Slit Lamp Biomicroscopy
 - Study eye only
 - Pre-injection
- IOP
 - Study eye only
 - Pre-injection
 - At least every 30 minutes after injection until normalized (within 5 mmHg of pre-injection measurement)
- Study Treatment IC Injection (SE) •
- Record Adverse Events and Concomitant Medication Use •

6.5.6 Day 21 ± 1

- Obtain Sample for ADA •
 - Pre-injection
- Obtain Sample for PK
 - Pre-injection
 - 1.5 hours after injection
- BCVA •
 - Study eye only
 - Between 07:00 AM and 11:00 AM
 - Pre-injection
- Specular Microscopy
 - Both eyes

- Pre-injection
- Slit Lamp Biomicroscopy
 - Study eye only
 - Pre-injection
- IOP
 - Study eye only
 - Pre-injection
 - At least every 30 minutes after injection until normalized (within 5 mmHg of pre-injection measurement)
- Study Treatment IC Injection (SE)
- Record Adverse Events and Concomitant Medication Use

6.5.7 Day 28 ± 1

- Obtain samples for Laboratory Testing (Chemistry, Hematology, Urinalysis, HbA1c)
- Obtain sample for ADA
- BCVA
 - Study eye only
 - Between 07:00 AM and 11:00 AM
- Specular Microscopy (including automated pachymetry)
 - Both eyes
- Slit Lamp Biomicroscopy
 - Study eye only
- IOP
 - Study eye only
- Record Adverse Events and Concomitant Medication Use

6.5.8 Day 56 ± 3

- Urine pregnancy (WOCBP)
- Obtain samples for laboratory testing (Chemistry, Hematology, Urinalysis, HbA1c)
- Obtain sample for ADA
- Obtain sample for PK
- NEI-VFQ-25
- BCVA
 - o Study eye only
 - Between 07:00 AM and 11:00 AM
- Specular Microscopy (including automated pachymetry)

 Both eyes
- Comprehensive Ocular Examination
 - Slit-lamp biomicroscopy
 - Dilated examination of lens, fundus, and vitreous. Note: dilation should be performed after BCVA and measurement of IOP.
 - Both eyes
- IOP
 - Study eye only
- Pentacam examination

- Both eyes
- Record Adverse Events and Concomitant Medication Use

6.5.9 Day 90 ± 7

- BCVA
 - Study eye only
 - Between 07:00 AM and 11:00 AM
- Specular Microscopy (including automated pachymetry)

 Both eyes
- Slit Lamp Biomicroscopy
 - Study eye only
- IOP
 - Study eye only
- Record Adverse Events and Concomitant Medication Use

